Overview: The proposed design is a mixed methods, interventional study with concurrent controls to examine the effects of an intervention to improve role concordance on decisional outcomes among newly diagnosed breast cancer patients. Providers will be blind to the patient's preferred decision making role in the first half of the study and then informed of the preferred role in the second half of the study. The intervention will be a short conversation that providers will have with patients at the beginning of the clinic visit where the provider identifies the patient's preferred role and their desire to help the patient achieve it. Quantitative comparisons before and after implementation of the intervention and qualitative analyses of the recorded clinical encounters will be performed to evaluate the effects of the provider directed behavioral intervention to improve role concordance. This study design was chosen because once the intervention is introduced providers may have difficulty omitting this behavior from the clinical encounter and this could confound our results. If patient-level randomization was used, providers would need much more oversight and coaching in order to not "forget" which patient is in which arm and the study effects may be biased toward the null. In this small study, if provider-level randomization was used, this could significantly bias assessments of patient involvement due to inherent differences in how the providers approach clinical interactions at baseline. Also, we do not anticipate substantial variability in the pre and post populations during the short time period of the study other than the date of their consultation and, thus, we expect that the populations will be very similar in other characteristics. We plan to examine differences between pre and post-intervention patients to evaluate this.

Objectives:

1. Investigate the impact of a brief provider-led intervention about the patients' preferred role in treatment decision making on role concordance. **We hypothesize that:**
 - a. Role concordance will be improved when the preferred role is discussed with the patient at the beginning of the encounter.
 - b. The provider's perception of the role achieved will be more concordant with the patient's perception when the preferred role is discussed.

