Intervention: The intervention will take place in the second half of the study, where the research assistant will inform the provider of the patient's preferred role based on the Patient Preference Scale prior to the clinic visit. The provider will then have a brief conversation at the beginning of the clinic visit where they state "I see that you prefer to have treatment decisions made (*together, by yourself, by me*) today. I appreciate knowing this information." The rest of the encounter will proceed as per the provider's usual practice. All other study procedures will be the same and the same perception scales will be used after the clinic visit and concordance and discordance will be examined as described in the study flow diagram.

Outcomes: The primary outcomes will be role concordance and patient satisfaction with the decision process. Secondary outcomes will be role perception concordance between provider and patient, quality of life at 2 to 6 weeks and 6 months after initial clinic visit, decision regret at 2 to 6 weeks and 6 months after initial clinic visit, and completion or planned completion of recommended therapies at 6 months. These time points were chosen to provide an early assessment of the impact of the intervention and to see if the results are durable after a longer period of time while still allowing us to conclude the study within the funding timeframe. There is evidence that decision regret is stable over time out to 4 years after diagnosis [4]. We will also correlate role

preference and concordance with surgical procedure performed or planned to look for associations between these measures and type of surgery received or planned, controlling for ineligibility for breast conservation.

Risks and Benefits of Participation: Participation is completely voluntary and may be withdrawn at any time. This is a low risk study, but some patients may experience distress from the questions on the surveys. If a patient experiences distress, she will be referred to our in-clinic Licensed Care Social Worker and she will make appropriate referrals to psychiatric care if necessary. There is also a low risk of loss of privacy and patients will be made aware of this. The benefits of participation are greater patient awareness of their own preferences and decisions.

Please see the study flow diagram on the following page.

Record decisions made and intentions
to complete therapy

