Data Management: All surveys will be administered electronically (tablets will be used for in clinic surveys) and stored on a secure University server. The surveys will be collected both in person (when the patient is in clinic) and electronically. The surveys will be built into and collected in the Research Subject Registry (RSR) database. Only study personnel will have access to the data and the PI will be responsible for deciding the role and level of access for each person. All digital audio recordings will be stored on a secure, password protected University computer in a locked office at Huntsman Cancer Institute. Again, only study personnel will have access to this data. The digital recordings will be transcribed and de-identified for coding and analysis. The de-identified transcripts will only be available to trained coders, the PI, and study coordinator. The electronic transcriptions will be stored on University based, password protected computers in the secured office area of the PI. Badge access is required to enter the office area during non-business hours. Paper versions will only be used if necessary due to computer outages or significant feasibility issues with the electronic transcripts and will be stored in a locked filing cabinet in the PIs locked office. Again, access will only be given to study personnel.

Statistical Analysis:

We are interested in evaluating whether patients play their desired role in treatment planning, and whether informing providers of patients' preferred roles improves patients' perception of achieving their desired role. Specifically, we will study two groups of patients, a non-intervention control group, where providers are blind to the patient's preferred decision making role and an intervention group where the provider is informed of the patient's preferred role. For this study we plan to enroll 100 patients, where the first 50 will be in the no intervention group and the next 50 will be in the intervention group. We expect the results to provide preliminary data for powering a larger extramural grant.

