The primary aim of our study (a) is to evaluate patient perception of whether the patient achieved his/her preferred role in the treatment decision. This aim will be met by estimating perception concordance between baseline and after the clinic visit within the intervention and control groups, and testing for group differences in concordance. A secondary goal (b) will be to similarly estimate concordance of provider's perception of the patient's preferred role versus the patient's perception of the achieved role (where both scales will be measured after the clinic visit). In addition, we also plan to test the following outcomes between groups: c) patient's satisfaction with the decision making process, d) FACT-B assessment of short-term QOL, e) decision regret, f) OPTION assessment of patient involvement and g) completion or intention to complete therapies. Finally, we will compare the patient role concordance estimated in a) with improved short-term and longer-term improvements in: outcomes c)-g). Specific methods corresponding to each analysis objective are described below.

a-b) Concordance measures. The patient and provider perception scales consist of 5 levels ranging from active to passive involvement in treatment decisions. Consistent with other similar studies [5-7], our primary concordance measure will be defined as exact agreement in patient responses between the baseline and post clinic visit. Within each group we will provide concordance rates and the associated 95% confidence interval (CI) using the Wilson Score interval approach. We will also report the weighted Kappa coefficient and its 95% CI. Group differences in concordance will be tested using a chi-squared or Fisher's exact test. As a sensitivity analysis for this assessment, we may adjust for potential confounders in a logistic framework predicting concordance. We will consider the following variables for adjustment if they are associated with the concordance outcome: age, education level, and stage of disease.

c) Patient's satisfaction with the decision making process. Satisfaction with the decision making process will be measured directly after the clinic encounter using a modified version of the Holmes-Rovner Satisfaction with

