Decision scale which combines several elements of decisional satisfaction and is designed to measure satisfaction with the decision regardless of prognosis or outcome [5, 8]. It also correlates with decision confidence. It uses a Likert-type ranking of 6 items related to the decision. The modified version will measure the satisfaction with the process of decision making rather than the decision itself. Group satisfaction differences will be assessed using a two-sample two-tailed t-test. We will also use linear regression to consider adjusting for the potential confounders described above (a-b) along with the following treatment related variables: type of surgery received and the sequencing of treatment (chemo first vs. surgery first), surgical complications, recommendation for chemotherapy, and recommendation for radiation treatment in these analyses. We will also compare satisfaction with concordance within groups using t-tests (or regression to adjust for covariates). Finally, we will test whether the relationship between satisfaction and concordance differs across groups using linear regression and testing for significance of a group*concordance interaction.

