d) Comparing FACT-B assessment of short-term QOL between the groups. Quality of life will be assessed using the Functional Assessment of Cancer Therapy-Breast (FACT-B) questionnaire. This scale will be used prior to the first consultation to establish a baseline for each patient and will subsequently be used at 2 to 6 weeks and 6 months after initial clinic visit. This questionnaire is a well validated tool for assessing quality of life in breast cancer patients. It measures 27 items in five different areas: physical well-being, social/family well-being, emotional well-being, functional well-being, and additional concerns specific to this patient population. It has been shown to have significant sensitivity for changes in performance status and quality of life [9]. We will compare the FACT-B assessment between the intervention and control groups using a linear mixed effects model framework with an unstructured covariance, adjusting for baseline FACT-B levels. The final time point (6 months) is our main time point of interest, but we will also estimate differences at 2 to 6 weeks. We will consider controlling for the covariates described in c). We will also compare FACT-B with concordance within groups using separate linear mixed effects models for each group. Finally, we will test whether the relationship between satisfaction and concordance differs across groups using linear mixed effects regression and testing for significance of a group*concordance interaction.

e) Decision regret. The decision regret outcome will be measured using the Decision Regret Scale which will also be administered at 2 to 6 weeks and 6 months after initial clinic visit. This scale has been used in modified version to assess for elements specific to breast cancer surgery and was found to have high internal consistency [4]. It is a 5 item scale with items ranked on a 5-point Likert-type scale and added together with higher score indicating more regret. The analysis framework for comparing groups will be similar to d), except that there is no baseline level to control for in the models.

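### Baseline FACT-B is collected before the visit but used only in the FACT-B model; it could also be a prespecified covariate for satisfaction and decision regret

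*Combined protocol and SAP*

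**What the plan says.** All references are to the combined protocol and SAP.

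- **Design.** The Statistical Analysis section states that "the first 50 will be in the no intervention group and the next 50 will be in the intervention group". The Overview expects the two populations to be similar and adds: "We plan to examine differences between pre and post-intervention patients to evaluate this". It names no variables for that check.
- **FACT-B.** Section d) says: "This scale will be used prior to the first consultation to establish a baseline for each patient". Table 2 confirms the pre-visit assessment. The group comparison in d) uses a "linear mixed effects model framework with an unstructured covariance, adjusting for baseline FACT-B levels". No other analysis names the baseline score.
- **Satisfaction.** Section c): "Satisfaction with the decision making process will be measured directly after the clinic encounter". Then: "Group satisfaction differences will be assessed using a two-sample two-tailed t-test". A linear regression follows in which adjustment will be considered for age, education and stage (from a-b) and for surgery type, treatment sequence, surgical complications, and chemotherapy and radiation recommendations.
- **Regret.** Section e): "The analysis framework for comparing groups will be similar to d), except that there is no baseline level to control for in the models". Because e) follows d), and d) allows the covariates in c), regret inherits the same optional list. Table 2 places regret only at 2 to 6 weeks and 6 months.
- **Status of satisfaction.** The Outcomes section says: "The primary outcomes will be role concordance and patient satisfaction with the decision process". The Statistical Analysis section makes concordance the primary aim and lists satisfaction among the further outcomes.

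**The concern.** Neither list of optional covariates holds a patient-reported score taken before the visit. Such a score exists for each patient, covers emotional well-being among other domains, and is left out of the satisfaction and regret analyses.

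This matters in two places. First, assignment is by calendar order, with 50 patients expected in the first year and 50 in the second, so nothing in the design balances well-being between groups. If the phases differ in well-being, and well-being is related to the outcome, the difference passes into the group contrast. Second, Objective 2 compares patients who did and did not achieve role concordance. Concordance is not assigned, so this comparison is observational even if the two phases match perfectly. Baseline distress could plausibly affect both the role a patient perceives and her later rating. A baseline covariate would limit both problems and could also reduce residual variance.

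**Working it through.** **The plan's own figure.** The only power statement concerns concordance: 80% power for a 28-point increase over 50%, with 50 per group and a two-sided Fisher's exact test at 0.05. Exact enumeration for 50% versus 78% gives 78.9%, which agrees. No power, SD or correlation is given for satisfaction or regret, so the figures below are in SD units and illustrative.

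**Inputs.** n = 50 per group and two-sided alpha 0.05 (documents); 80% power for a mean difference (assumed here, matching the concordance calculation); r, the correlation between baseline FACT-B and the outcome, from 0 to 0.5 (assumed); D, the systematic difference between phases in mean baseline FACT-B, 0.3 SD (assumed).

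**Precision.** The standard error of a mean difference is sqrt(2/50) = 0.2 SD. The detectable difference for the two-sample t-test at 80% power is 0.566 SD (0.560 by the normal approximation). With the covariate, residual variance is multiplied by 1 - r², the detectable difference by sqrt(1 - r²), and the equivalent sample size per group is 50/(1 - r²).

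**Bias.** The unadjusted contrast shifts by r × D. The rejection rate under a true null is P(|Z + rD/0.2| > 1.96). For r = 0.5: shift 0.15 SD, 0.15/0.2 = 0.75 standard errors, and P(Z > 1.21) + P(Z < -2.71) = 0.113 + 0.003 = 11.7% from unrounded values.

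| r | Variance reduction | Equivalent n per group | Detectable difference (SD) | Bias at D = 0.3 SD | Unadjusted type I error |
|---|---|---|---|---|---|
| 0 | 0% | 50 | 0.57 | 0 | 5% |
| 0.2 | 4% | 52 | 0.55 | 0.06 SD | 6.0% |
| 0.3 | 9% | 55 | 0.54 | 0.09 SD | 7.3% |
| 0.4 | 16% | 60 | 0.52 | 0.12 SD | 9.2% |
| 0.5 | 25% | 67 | 0.49 | 0.15 SD | 11.7% |

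**What the last column means.** It requires D to be a real difference between the populations seen in the two phases. If 0.3 SD were only the observed sample difference, the conditional standard error would be 0.2 × sqrt(1 - r²), and the rejection rate would be 5.6% at r = 0.2 and 8.2% at r = 0.5. Chance imbalance alone, which lies within ±1.96 × 0.2 = ±0.39 SD 95% of the time, does not raise the unconditional type I error.

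**The case against.** The strongest reply is that the plan contains no error here. Regret and process satisfaction cannot be rated before the decision, so the sentence in e) is correct, and FACT-B measures a different construct. This stands: the point is an inexpensive improvement, not a contradiction.

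A reader might infer that satisfaction and regret are compared with no adjustment at all. The documents do not support that. Section c) plans a regression beside the t-test, its satisfaction-by-concordance comparison also allows regression, and regret inherits the covariate list through d). What remains is that this adjustment is discretionary and names no pre-visit patient-reported score. Several listed variables, such as surgery received and complications, arise after the visit and cannot stand in for a baseline; satisfaction is already recorded by then.

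A reader might also infer that the type I error of these tests is about 12%. That needs a systematic 0.3 SD difference between phases together with r = 0.5. The documents give evidence for neither, and the Overview expects similar populations. The satisfaction scale is described as designed to measure satisfaction independently of prognosis or outcome, so a low correlation is quite possible.

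Finally, the study is meant to supply preliminary data for a larger grant, claims no power for either outcome, and treats regret as secondary. That limits the weight of the point. It does not argue against using a covariate already in hand.

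**Conclusion.** The point holds as a modest, low-cost improvement. Baseline FACT-B is collected on each patient and used only in the FACT-B model, although satisfaction and regret are compared across consecutive non-randomised phases and by unassigned concordance status.

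Its size is uncertain. Over an assumed r of 0 to 0.5, the detectable difference goes from 0.57 SD (no gain) to 0.49 SD. Under an assumed systematic phase difference of 0.3 SD, the bias removed is 0 to 0.15 SD, and the type I error without adjustment is 5% to about 12%. Adjustment removes only the part of a phase difference that baseline FACT-B carries; calendar-time effects stay.

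Calling satisfaction co-primary would rest on the Outcomes section alone, since the Statistical Analysis section places it among additional outcomes. The two should be reconciled, but the point does not depend on which is right.

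**What to change.** 1. **Section e).** Keep the statement that regret has no baseline of its own, and prespecify baseline FACT-B total score as a covariate in the regret models.
2. **Section c).** Add baseline FACT-B total to the linear regression already planned, and report that adjusted group difference beside the t-test.
3. **Concordance analyses.** Include baseline FACT-B in the satisfaction-by-concordance and regret-by-concordance models.
4. **Comparability check.** Name baseline FACT-B among the variables compared between the two phases.

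The cost is SAP wording, one degree of freedom per model, and a stated rule for the patients without a baseline score (simple imputation, or omission from the adjusted model). No new data are needed.

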2. Investigate the impact of role concordance in the treatment decision making process on short term and long term quality of life and decision outcomes. **We hypothesize that:**
 - a. Patients who achieve role concordance will be more satisfied with the decision process.
 - b. Patients who achieve role concordance will have better QOL and less decision regret at early (2 to 6 weeks) and later (6 months) timepoints after the clinic visit.
 - c. Patients who achieve concordance will be more likely to complete or plan to complete recommended treatments.

Study Subjects: The study population will be newly diagnosed female breast cancer patients scheduled to see one of four breast surgeons at the Huntsman Cancer Hospital Breast Surgery Clinic at the University of Utah. We will exclude patients who have had breast cancer previously, cannot read or write, or have a primary language other than English.

Recruitment: All newly diagnosed patients scheduled in our clinic will be given a recruitment letter as part of their new patient materials (sent the day they scheduled their appointment). They will then be called the day before their visit to gauge interest in participation. If they express interest, they will be sent a consent form electronically so that they can familiarize themselves with the study. They will be asked to arrive at least 30 minutes early for their scheduled appointment (most patients do this anyway) and will be met by a research assistant who will explain the study again and obtain written consent. This same assistant will administer the study scales before and after the clinic visit. Providers will not consent patients nor administer any patient assessments for the study because they will also be delivering the intervention. We expect to enroll a total of 100 patients with 50 in the first year and 50 in the second. We see over 400 new breast cancer patients per year and therefore need approximately 12% of these patients per year to participate in order to reach our recruitment goals. Prior studies using similar methods have had excellent enrollment rates with 98% of eligible patients interested in enrollment.

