I prefer that my doctor make the final decision about which treatment will be used but seriously consider my opinion.	My doctor made the final decision about which treatment would be used but seriously considered my opinion.	I made the final decision about which treatment the patient would receive after seriously considering the patient's opinion.
I prefer to leave all decisions regarding my treatment to my doctor.	My doctor made all the decisions regarding my treatment.	I made the final decision about which treatment the patient would receive.

Recording of clinical consultations has been well-studied as a tool for determining patient-centered communication [1-3]. Therefore, all clinic encounters will be digitally recorded, transcribed, and analyzed using the OPTION scale for patient involvement, which is described below. The transcriptions will be de-identified and coded by independent raters (paid graduate students).

Assessments of QOL and decision regret will be performed at early (2 to 6 weeks) and later (6 months) timepoints after the clinic visit. These scales will be distributed electronically and patients will receive a phone call from the study coordinator to remind them to complete the measures. If they have not completed the measures by one week from the reminder phone call, a second call will be placed with an offer to complete the surveys over the phone with the study coordinator.

Chart review of all participants will be reviewed at the 6 month time point to assess for decisions ultimately made and completion or intention to complete recommended therapies. This timeframe was selected because the majority of patients will have completed their surgery, chemotherapy (if needed), and radiation (if needed) or at least have the initiation of these therapies planned. Radiation is always given last and this therapy is the most likely to still be in the planning stages. Also at this time point, endocrine therapy will have been initiated by some patients and may be planned by others.

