f) OPTION assessment of patient involvement. The outcome of patient involvement at the clinic encounter will be measured using the OPTION scale. This scale was developed to measure the extent to which providers involve patients in decisions. A description of the measures used and timeline is illustrated in Table 2. With this scale, 2 independent raters will use a 12 item list to code and score a clinical consultation. It provides a reliable method for detecting differences between the extent of patient involvement with good inter-rater reliability and inter-rater agreement [10, 11]. Raters will be hired graduate students who will be trained in this method, with each rater coding and scoring the first 10 transcripts followed by comparison of the results using the intraclass correlation coefficient (ICC) and its 95% CI before switching to a single rater per transcript method. These scores will be compared between the intervention and control groups for differences in patient involvement using a two-sample t-test and linear regression to adjust for the covariates described in c). We will also compare patient involvement with concordance within groups using t-tests (or regression to adjust for covariates). Finally, we will test whether the relationship between involvement and concordance differs across groups using linear regression and testing for significance of a group*concordance interaction.

g) *Completion or intention to complete therapies.* Group differences in completion or intention to complete recommended therapies will be assessed at 6 months after the clinic visit through chart review of all participants' charts. Intent will be defined as initiation or scheduled initiation of a recommended treatment. The variables of decision made (i.e. type of surgery or sequence of therapy) and completion or intention to complete recommended therapies will be compared between groups using a chi-squared or Fisher's exact test. We will also use a logistic regression framework to test whether the relationship between concordance with completion differs by group. We will consider adjusting for a few covariates described in c), keeping in mind a minimum of 5-10 events per predictor in our models. [12]

Table 2.

Measure Name	Assesses	Prior to Clinic Visit	Immediately After Clinic Visit	2 to 6 Weeks After Clinic Visit	6 Months After Clinic Visit
Patient Preference Scale	Patient's preferred role in decision making process	X			

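### Intent is defined as starting or scheduling a treatment, so a patient who starts a recommended therapy and abandons it before the 6-month chart review is scored as a success

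*Combined protocol and SAP*

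**What the plan says.** Hypothesis 2c (Objectives) reads: "Patients who achieve concordance will be more likely to complete or plan to complete recommended treatments". The Outcomes paragraph lists the matching secondary outcome as "completion or planned completion of recommended therapies at 6 months".

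Statistical Analysis, g) says that group differences in this outcome "will be assessed at 6 months after the clinic visit through chart review of all participants' charts". It then gives the scoring rule: "Intent will be defined as initiation or scheduled initiation of a recommended treatment". The test follows: "completion or intention to complete recommended therapies will be compared between groups using a chi-squared or Fisher's exact test". A logistic model is also planned, to see whether the link between concordance and completion differs by group.

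Methodology explains why therapy that is not yet finished has to count. By 6 months most patients are expected to have finished surgery, chemotherapy and radiation where needed, "or at least have the initiation of these therapies planned". Radiation is the therapy most likely to be still in planning, and "endocrine therapy will have been initiated by some patients and may be planned by others".

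No section says how to score a therapy that was started and then stopped.

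**The concern.** The hypothesis is about completing treatment or planning to complete it. The scoring rule asks only whether treatment was started or booked. The two part company for one kind of patient: she began a recommended therapy and gave it up before the chart was read. She fails both halves of 2c, yet starting alone satisfies the definition of intent.

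Two things are at stake. The reported completion rate is too high by the proportion of such patients. If they are also more frequent among discordant or control patients, the difference that the study wants to see is partly erased. The study is meant to supply preliminary data for powering a larger grant, so an inflated rate would carry forward.

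**Working it through.** **The plan's own power figure.** The only stated power is for role concordance: 80% for a 28-point increase from 50%, with 50 per group, two-sided Fisher's exact test at 0.05. Exact enumeration over the two binomial distributions at 50% and 78% gives 78.9%, so the figure reproduces to within about a point. No power is stated for outcome g. The same enumeration is used below.

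**What the rule does to the rate.** For each group let p be the true proportion who completed or still plan to complete, and a the proportion of all patients in the group who started and then abandoned therapy. The rule records

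observed success = p + a,

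so the observed difference is (p1 − p0) + (a1 − a0). The rate is always raised by a. The difference shrinks only if a0 > a1, where group 0 has the lower true completion.

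**Illustration 1: the same share of non-completers had started and stopped.** The documents give no completion or abandonment rates. Assume p0 = 70% and p1 = 92%, with 50 per group (the plan's allocation). If a share f of non-completers had started and stopped, then a = f(1 − p) and the observed difference is (1 − f)(p1 − p0).

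| f | Observed rates | Difference (points) | Fisher power | Expected non-successes in 100 |
|---|---|---|---|---|
| 0 | 70% vs 92% | 22.0 | 75.6% | 19.0 |
| 10% | 73% vs 92.8% | 19.8 | 68.5% | 17.1 |
| 25% | 77.5% vs 94% | 16.5 | 56.0% | 14.25 |
| 50% | 85% vs 96% | 11.0 | 31.5% | 9.5 |
| 75% | 92.5% vs 98% | 5.5 | 7.4% | 4.75 |

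For f = 50%: 70 + 0.5 × 30 = 85; 92 + 0.5 × 8 = 96; 96 − 85 = 11.

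Starting from 70% and 90% gives the same pattern: power 64% at f = 0, then 45%, 24% and 6% at f = 25%, 50% and 75%.

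**Illustration 2: equal absolute abandonment.** Add 4 points to each group: 74% vs 96%. The difference stays at 22 points and power rises to 84.5%. The rates are still inflated, but the comparison is not diluted.

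**Events for the logistic model.** Section g asks for at least five to ten events for each predictor. Group, concordance and their interaction are three predictors, so 15 to 30 events. In Illustration 1 the rarer category has 19 at f = 0, which meets the lower figure, and 14.25 at f = 25%, which does not.

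**Group sizes for 2c itself.** Hypothesis 2c compares concordant with discordant patients, whose numbers are not fixed. At the plan's figures of 50% and 78% concordance they would be 25 + 39 = 64 and 36. For 90% vs 70%, power is 66% with that split and 64% with 50 each, so the split matters little here.

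**The case against.** The strongest reply is that the composite is deliberate. At 6 months many therapies can only be under way or booked, and starting or scheduling is something a chart shows. That stands: counting ongoing and scheduled therapy is consistent with 2c and is not an error. It does not extend to therapy that the chart shows was abandoned.

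A second reply is that the sentence is merely silent on stopping, and a sensible abstractor would code a documented stop as no longer intending to complete. That abstractor would be departing from the written definition, which initiation alone satisfies. Different abstractors could also score the same chart differently.

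Three stronger readings are tempting, and the documents do not support them:

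- A reader might infer that any true difference must shrink. Illustration 2 shows that it need not. Shrinkage requires more abandonment, in absolute terms, in the group with lower completion. That is plausible under 2c, but no figure in the plan shows it.
- A reader might infer from the singular wording of the intent sentence that one started treatment is enough, even if another is declined. The sentence can equally be read as defining intent for each treatment in turn, and the outcome itself is repeatedly worded in the plural. This is an ambiguity to settle, not a stated rule.
- A reader might take the low end of the power range as a forecast. The rates and shares are assumed; at a 10% share the loss is about 7 points.

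**Conclusion.** The point holds in a limited form. The definition of intent is looser than hypothesis 2c and scores abandoned therapy as success. Inflation of the completion rate follows from the text alone wherever any patient abandons therapy. Dilution of the comparison is conditional on where abandonment is more common. Its size cannot be derived from the documents: under the assumed 70% and 92%, power falls by about 7, 20 or 44 points at shares of 10%, 25% or 50% (75.6 − 68.5, 75.6 − 56.0, 75.6 − 31.5), and does not fall if absolute abandonment is equal.

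The outcome is secondary, carries no power claim, and sits in a study described as preliminary. Neither primary outcome is affected. The change is still worth making, because it is cheap and the information should be in charts that will be read anyway.

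**What to change.** At the planned 6-month chart review, code each recommended therapy for each patient as one of: completed; ongoing; scheduled; stopped early by patient choice; stopped early on the treating team's advice; declined or not started.

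Replace the sentence defining intent with a rule to this effect:

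- Success means that every recommended therapy is completed, ongoing or scheduled.
- Stopping by patient choice, and declining, are non-success.
- A stop on the treating team's advice is not scored as patient non-completion. The SAP should say in advance how it enters the outcome, for instance by treating that therapy as no longer recommended for that patient.

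Report the present initiation-based definition as a sensitivity analysis, with counts in each code by group and by concordance.

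The cost is SAP and abstraction-form wording, slightly more abstraction time and a less favourable completion rate. The chart review already covers every participant, and no visit or patient assessment is added. Where the chart does not record why a therapy stopped, the abstraction form needs an unknown code and the SAP needs a stated way of handling it.
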